### **3.2.5 Allowed Concomitant Medication**

It is mandatory that all doses of all RA medications (MTX, steroids and NSAIDs) taken during the first 24-week period (Part A) must remain stable.

Patients will continue to take their usual prescribed concomitant medications as allowed by the protocol, including MTX (7.5 to 25 mg/week) and folic or folinic acid, from their usual source, according to local standards and availability.

All patients should also continue to receive if there is any background oral corticosteroids ( $\leq 10$  mg/day prednisone or equivalent) or NSAIDs. During the 4 weeks (for oral corticosteroids) or 3 weeks (for NSAIDs) prior to Day 1, the doses must remain stable.

If clinically required for safety reasons, modifications to doses of MTX, corticosteroids and NSAIDs will be allowed. The Investigator must use the procedures outlined below in making modifications to these medications and document all changes and the reason for the changes should be documented in the patient's electronic case report form (eCRF).

**Methotrexate:** Dose of MTX should remain stable throughout the study. Reductions for MTX dose or a change of route of administration may be performed after visit at Week 24 for safety reasons only.

Lower doses of MTX ( $< 10$  mg/week) are only permitted if patients have a documented evidence of intolerance to higher doses of MTX.

If dose reduction is a result of intolerance, such intolerance must be recorded as an AE and the dose modification recorded in the eCRF.

**Oral corticosteroids:** If receiving current treatment with oral corticosteroids (other than intra-articular or parenteral corticosteroids), the dose must not exceed 10 mg/day prednisone or equivalent. The dose should remain stable from 4 weeks prior to randomization throughout the study. From Visit 12 at Week 24, reductions in these treatments will be allowed only for safety reasons. Increases in corticosteroids for treatment of RA are not allowed over the study period and should be avoided. To treat non-RA conditions, increased doses of oral corticosteroids, up to 40 mg of prednisone daily (or

equivalent), for 2 weeks or less will be permitted. The corticosteroid dose should be tapered down to the previous level as rapidly as medically possible.

**NSAIDs:** Patients may be treated with NSAIDs, up to the maximum recommended dose, (including cyclooxygenase-2 inhibitors) throughout the study. The choice and doses of NSAIDs used to treat patients are at the discretion of the Investigator. Patients on NSAIDs at Screening should continue at a stable dose from 3 weeks prior to randomization throughout the study. The dose and type of NSAID may be changed after Visit 12 at Week 24 of the study. Aspirin may be taken to reduce cardiovascular risk, but should not exceed 350 mg/day. NSAIDs or other analgesics for treatment of conditions other than RA may be used for short periods not exceeding 7 days.

### **3.2.6 Rescue Therapy**

From Week 16, patients who have less than a 20% improvement in both tender and swollen joint counts compared to Baseline (<ACR20) may receive “rescue” treatment with one non-biologic DMARD. The patient will be discontinued from the study treatment and the choice of DMARD is at the discretion of the Investigator, but could be hydroxychloroquine or sulfasalazine. Patients receiving “rescue” medication attend all visits until week 52.

The following medications are not permitted for use as “rescue” treatment: azathioprine, mycophenolate mofetil, cyclophosphamide, cyclosporine or any biologic agent. Any patient requiring medication mentioned above, should be discontinued from study treatment but will attend all visits until week 52.

### **3.2.7 Management of Hepatitis Reactivation and Other Infections During Rituximab Therapy**

Patients with HBV DNA >20 IU/ml are ineligible as per exclusion criteria. Patients who show evidence of prior hepatitis B infection may participate in the study following consultation with a hepatitis expert regarding monitoring and use of HBV antiviral therapy, and provided that they agree to undergo monthly PCR HBV DNA testing during treatment and to receive treatment as indicated. During the study, a HBV re-test will be performed monthly including Day 1, Weeks 4, 8, 12, 16, 20, 24, 36, 52, or unscheduled visit if required.

Patients will receive HBV antiviral prophylaxis therapy and be monitored as recommended by hepatitis experts. HBV reactivation has been reported up to 24 months following completion of rituximab therapy. If a patient develops reactivation of HBV or any other significant infections while on rituximab, the Investigator should immediately discontinue study drug, consult with hepatitis experts, and institute appropriate treatment. For details and management of other infections, refer to the current marketed rituximab prescribing information.

### **3.3 Study Population**

Patients with RA who have had an inadequate response (at least 3 months' treatment according to the approved treatment and dosage of each TNF inhibitor) or intolerance (at Investigator's discretion and/or experience of intolerable AE such as infusion related reaction, hypersensitivity, anaphylaxis or severe toxicity) to one or more anti-TNF therapies.

### **3.4 Eligibility Criteria**

#### **3.4.1 Informed Consent**

Patients must have the ability and willingness to provide written informed consent, prior to any study-specific procedures, and to comply with the requirements of the protocol.

#### **3.4.2 Inclusion Criteria**

Patients are required to meet the following inclusion criteria:

- |   |
|---|
| 

1. Male or female outpatient, between 18 and 80 years of age at Screening.

2. Severe RA defined as:

• Diagnosis of RA according to the revised (1987) ACR criteria for the classification of RA for at least 3 months prior to screening visit (see Appendix 3).

• And <math>\geq 6</math> swollen joints and <math>\geq 6</math> tender/painful joints (from the 66/68 joint count system).

• And C-reactive protein (CRP) <math>\geq 1.0</math> mg/dL or an ESR <math>\geq 28</math> mm/hour at Screening.

• And positive RF (<math>\geq 20</math> units/mL) or anti-CCP antibodies (<math>\geq 10</math> units/mL) at Screening.

3. Patients with severe RA who have had an inadequate response to at least 3 months' treatment (according to the approved treatment and dosage) or intolerance (at Investigator's discretion and/or experience of intolerable AE or toxicity such as infusion related reaction, hypersensitivity, anaphylaxis or severe toxicity) to anti-TNF therapy (experience of severe AE or toxicity).

 |
|---|

4. Current treatment for RA on an outpatient basis:
- Receiving MTX 7.5 - 25mg/week (oral or parenteral) for at least 12 weeks, including the last 4 weeks prior to Day 1 at a stable dose, via the same route of administration, dose, and formulation. Patients receiving a lower dose of MTX (<10 mg/week), stable for 4 weeks prior to Day 1, should be doing so as a result of a documented evidence of intolerance to higher doses of MTX.
  - Leflunomide must be withdrawn at least 12 weeks prior to Day 1 or a minimum of 4 weeks prior to Day 1 if after 11 days of standard cholestyramine washout.
  - All DMARDs different from MTX and leflunomide must be withdrawn at least 4 ~ 8 weeks as described in Table 4 prior to Day 1.
  - If receiving current treatment with oral corticosteroids, the dose must not exceed 10 mg/day prednisone or equivalent. During the 4 weeks prior to Day 1 the dose must be stable.
  - The most recent IM/intra-articular steroid injection should be  $\geq 6$  weeks prior to Day 1.
  - If receiving current treatment with NSAIDs at the time of Screening, the patient must remain on a stable dose for at least 3 weeks prior to Day 1.
  - Patients are willing to receive oral folic or folinic acid or equivalent during the entire study (mandatory co-medication for MTX treatment), according to local standards and availability.
- 5 Men and women of childbearing potential must use highly effective methods of contraception during the course of the treatment period and for at least 12 months after the last infusion of study drug. A man or woman is of childbearing potential if, in the opinion of the investigator, he or she is biologically capable of having children and is sexually active. Examples of highly effective contraception include:
- combined (estrogen and progestogen containing) hormonal contraception associated with inhibition of ovulation :
    - oral
    - intravaginal
    - transdermal
  - progestogen-only hormonal contraception associated with inhibition of ovulation :
    - oral
    - injectable
    - implantable 
  - intrauterine device (IUD) 
  - intrauterine hormone-releasing system (IUS) 
  - bilateral tubal occlusion 
  - vasectomised partner 
  - sexual abstinence 
-  Hormonal contraception may be susceptible to interaction with the study drug, which may reduce the efficacy of the contraception method.
-  Contraception methods that in the context of this guidance are considered to have low user dependency.
-  Vasectomised partner is a highly effective birth control method provided that partner is the sole sexual partner of the study participant and that the vasectomised partner has received medical assessment of the surgical success.
-  In the context of this guidance sexual abstinence is considered a highly effective method only if defined as refraining from heterosexual intercourse during the entire period of risk associated with the

study treatments. The reliability of sexual abstinence needs to be evaluated in relation to the duration of the clinical trial and the preferred and usual lifestyle of the subject.

- 6 Female patients of childbearing potential must have a negative serum pregnancy test at Screening (Visit 1) and a negative urine pregnancy test at each applicable visit thereafter. Females will be considered to be of non-childbearing potential if they fulfill one of the following criteria at Screening:
- Postmenopausal defined as amenorrheic for at least 12 months following cessation of all exogenous treatments
  - Documentation of irreversible surgical sterilization by hysterectomy, bilateral oophorectomy or bilateral salpingectomy but not tubal ligation

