### **3.2.3 Study Drug Administration (Part B)**

Patients with active rheumatoid arthritis (<50% improvement from Baseline in both the swollen and tender joint counts) who have been followed up during Part A will be provided with continued (or additional) treatment of rituximab.

Before subsequent dose, absolute neutrophil count must be  $\geq 1.5 \times 10^9/L$  and platelet counts must be  $\geq 75 \times 10^9/L$ . If the Absolute Neutrophil Count (ANC) value and platelet count are marginally lower, re-testing at an unscheduled visit may be performed at the discretion of the Investigator within the 4-week period between Week 20 and Week 24. In case Visit 11 is missed, all safety evaluations including ANC value and platelet count must be completed as an unscheduled visit for patient to be eligible for second course of infusion.

Eligible patients in the SAIT101 arm will receive additional SAIT101 treatment at Week 24 and Week 26. Eligible patients in the MabThera® arm will receive additional MabThera® treatment at Week 24 and Week 26. Eligible patients in the Rituxan® arm will be randomized in a 1:1 ratio to receive SAIT101 or Rituxan® treatment at Week 24 and Week 26.

Patients who develop an infusion reaction during the second course of treatment should be managed as described in Section 3.2.1.

Patient who are not eligible for the second course of study drug will also attend all visits after Week 24.

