### 3.4.3 Exclusion Criteria

Patients will be excluded if they meet any of the following exclusion criteria:

- 1 Females who are pregnant, breastfeeding, or planning a pregnancy during the Treatment Period of and 12 months after the last infusion of study drug.
- 2 Class IV as per the Classification of Global Functional Status in Rheumatoid Arthritis (as per ACR 1991 Revised Criteria) (see Appendix 4) or wheelchair/bed-bound.
- 3 History of or current inflammatory joint disease other than RA (including but not limited to gout, reactive arthritis, psoriatic arthritis, seronegative spondyloarthropathy or Lyme disease).
- 4 History of or current systemic autoimmune disorder (including but not limited to systemic lupus erythematosus, inflammatory bowel disease, pulmonary fibrosis, Felty syndrome, scleroderma, inflammatory myopathy, fibromyalgia, juvenile idiopathic arthritis, mixed connective tissue disease, vasculitis or other overlap syndrome), with the exception of the secondary Sjögren's syndrome.
- 5 Primary or secondary immunodeficiency (history of, or currently active), including known history of human immunodeficiency virus (HIV) infection or positive test at screening.
- 6 History of opportunistic infection.
- 7 History of deep space/tissue infection (e.g., fasciitis, abscess, osteomyelitis) and infected prosthetic joint.
- 8 Active infection of any kind (excluding fungal infection of nail beds) or any major episode of infection requiring hospitalization or treatment with i.v. anti-infective agents within 4 weeks prior to Screening or oral anti-infective agents within 2 weeks prior to Screening or use of antibiotic therapy three or more times in the last six months prior to Screening
- 9 Positive serological test for hepatitis B surface antigen (HBsAg), hepatitis B core antibody (HBcAb) or hepatitis C serology.
  - Patients with a negative HBsAg and positive HBcAb must have a hepatitis B virus (HBV) deoxyribonucleic acid (DNA) level <20 IU/mL (or 112 copies/mL) by polymerase chain reaction (PCR). These HBV patients must be willing to undergo monthly PCR HBV DNA testing during treatment and may participate following consultation with a hepatitis expert regarding monitoring and use of HBV antiviral therapy, and provided they agree to receive treatment as indicated. An HBV re-test will be performed monthly including Day 1, Weeks 4, 8, 12, 16, 20, 24, 36, 52, and unscheduled visit if required.

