### 3.6.1.2 Study Drug Administration Part A

Prior to Day 1, patients will be discontinued from their current anti-TNF medication, other biologic DMARDs or non-biologic DMARDs, except MTX.

The following must be performed on **Baseline (Day 1, Week 0)**:

Review inclusion and exclusion criteria and confirm patient eligibility. If eligible, the following procedures should be performed:

- Physical examination and vital signs;
- Neurological examination;
- Documentation of concomitant medications;
- Assessment of AEs/SAEs/ADRs;
- Urine pregnancy test for applicable female;
- Randomization to one of the study drugs;
- Contact IXRS.

The following efficacy assessments will be performed:

- Patient's assessment: global VAS and HAQ-DI, including patient's pain VAS;
- Physician's assessment: global VAS;
- Joint assessment. Each of the 66/68 joints will be evaluated for tenderness and swelling.

The following laboratory assessments will be performed:

- Clinical chemistry, hematology, urinalysis and HBV DNA only when negative HBsAg and positive HbcAb at screening;
- CRP, ESR;
- PK and PD sample collection;
- Immunogenicity.

The following must be also performed:

- The first of the two infusions of the study drug, as per IXRS.

The following must be performed on **Day 3 (Week 0)**:

- Physical / Neurological examination;
- Documentation of concomitant medications;
- Assessment of AEs/SAEs/ADRs;
- PK and PD sample collection.

The following must be performed on **Day 8 (Week 1)**:

- Physical / Neurological examination;
- Documentation of concomitant medications;
- Assessment of AEs/SAEs/ADRs;
- PK and PD sample collection;
- Immunogenicity.

The following must be performed on **Day 15 ± 1 day (Week 2)**:

- Physical examination and vital signs;
- Neurological examination;
- Documentation of concomitant medications;
- Assessment of AEs/SAEs/ADRs;
- Urine pregnancy test for applicable female;
- Contact IXRS;
- The second of the two infusions of study drug, as per IXRS;
- Clinical chemistry, hematology, urinalysis
- PK and PD sample collection;

- Immunogenicity.

The following must be performed on **Day 17 ± 1 day (Week 2)**:

- Physical / Neurological examination;
- Documentation of concomitant medications;
- Assessment of AEs/SAEs/ADRs;
- PK and PD sample collection.

The following must be performed on **Day 29 ± 3 days (Week 4)**:

- Physical / Neurological examination;
- Documentation of concomitant medications;
- Assessment of AEs/SAEs/ADRs.

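### Criterion 5 makes childbearing potential depend on sexual activity, so a fertile patient judged not sexually active falls outside the contraception rule and its abstinence check

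*Protocol*

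**What the plan says.** Protocol 3.4.2, criterion 5, requires contraception during treatment and for at least 12 months after the last infusion. The duty falls on patients of childbearing potential, and a patient of either sex is in that class if, in the investigator's opinion, "he or she is biologically capable of having children and is sexually active". Sexual abstinence is one of the listed methods. Footnote 4 accepts it only when it is maintained throughout the risk period, and adds: "The reliability of sexual abstinence needs to be evaluated in relation to the duration of the clinical trial and the preferred and usual lifestyle".

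Criterion 6 requires pregnancy tests of women of childbearing potential and carries its own female definition: "Females will be considered to be of non-childbearing potential if they fulfill one of the following criteria at Screening". Two conditions follow:

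- The first route is menopause, worded as "Postmenopausal defined as amenorrheic for at least 12 months following cessation of all exogenous treatments".
- The second route is surgery, and here the protocol asks for "Documentation of irreversible surgical sterilization by hysterectomy, bilateral oophorectomy or bilateral salpingectomy but not tubal ligation".

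Neither mentions sexual activity. Exclusion criterion 1 (3.4.3) separately bars "Females who are pregnant, breastfeeding, or planning a pregnancy during the Treatment Period" and for 12 months after the last infusion. It applies to women only.

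**The concern.** One section uses the same term in two ways. In criterion 5 it mixes fertility with current behaviour; in criterion 6 it is purely biological. The two part company for a fertile patient whom the investigator judges not to be sexually active.

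For that patient, not having intercourse is in effect the means of avoiding pregnancy. Footnote 4 was written to make that means dependable, by requiring a commitment for the whole risk period and a judgement on whether the commitment is credible. Criterion 5's definition removes the patient from the class to which the footnote attaches. At stake is an unplanned pregnancy during exposure in someone who entered without that evaluation. Exclusion 1 deals with planned pregnancy, and only in women. Stopping treatment for pregnancy (3.7.3) and reporting it (5.5) act only once it has happened.

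**Working it through.** No sample size, power, alpha or event figure bears on this point, so the check is a comparison of texts. Each rule is applied to the same patients.

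| Patient | Criterion 5: childbearing potential? | Contraception duty | Footnote 4 evaluation | Criterion 6: pregnancy tests? |
|---|---|---|---|---|
| Fertile woman, sexually active | Yes | Yes | Required if abstinence is the chosen method | Yes |
| Fertile woman, judged not sexually active | No (second condition fails) | No | Not required | Yes (neither exemption met) |
| Postmenopausal or surgically sterilised woman | No | No | Not applicable | No |
| Fertile man, sexually active | Yes | Yes | Required if abstinence is the chosen method | Not applicable |
| Fertile man, judged not sexually active | No (second condition fails) | No | Not required | Not applicable |

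1. Criterion 5 joins two conditions with *and*. Failing either one takes the patient out of the class, and the duty is placed only on that class.
2. Footnote 4 is attached to abstinence as one of criterion 5's methods. A patient with no duty to use a method has no method to evaluate, so the footnote is not triggered.
3. Criterion 6 says *if*, not *only if*. Treating its two conditions as the full list is therefore the natural reading and not an express rule. Two things favour it: no third condition appears anywhere in the documents, and the explicit refusal of tubal ligation marks the list as deliberately narrow.
4. On that reading the second row is contradictory: the woman is outside the class in criterion 5 and inside it in criterion 6.
5. For men there is no second definition. The last row is not a contradiction, but footnote 4 is bypassed for the same reason.
6. Criterion 5 also works against itself. It offers abstinence as a method, yet places the duty only on people currently judged sexually active. Someone already abstaining at entry is the one left out.

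**The case against.** The best answer is that the two criteria can be reconciled. Abstinence is a listed method, and footnote 4 judges it by usual lifestyle, which suits habitually inactive people. Reading criterion 5 to exclude them nearly empties the method. The investigator has also already formed an opinion on sexual activity. This stands as far as showing that a site may apply footnote 4 to such a patient, and many might. But the site would have to set aside the stated definition to do so, nothing obliges it to, and the opinion criterion 5 asks for concerns present activity, not reliability over the risk period.

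A second answer is that the criteria serve different purposes, contraception in one and testing in the other, so the woman is still tested. That is right on the natural reading of criterion 6. It limits the consequence, but a pregnancy test detects pregnancy and does not prevent it.

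A reader might also infer more than the documents support:

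- **That the wording removes later checks.** Day 1 is the last visit whose list says "Review inclusion and exclusion criteria and confirm patient eligibility", and the haematological clearance for the second course in 3.2.3 ("Before subsequent dose, absolute neutrophil count must be" above a threshold, with a platelet limit) says nothing on contraception. But no later visit list names a contraception re-check for any patient, on any method. That is a general feature of the schedule.
- **That the harm can be measured in weeks without cover.** The contraception period, including the part after the Week 52 visit for retreated patients, is the same for everyone of childbearing potential. Its length does not measure the effect of this wording.
- **That the duty is lost for good.** Criterion 5 is in the present tense and, unlike criterion 6, is not fixed at Screening. The duty would attach if the patient became sexually active.
- **That pregnancy tests are missed.** This would happen only if a site carried criterion 5's definition into Table 2 footnote i, section 3.6.5.6 or the visit lines for applicable females. Table 3 also lists hCG under chemistry and urinalysis. A count of tests is no measure of harm.

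**Conclusion.** The point holds as a defect in eligibility wording. As written, criterion 5 takes fertile patients judged not sexually active out of the contraception requirement, and with it out of any obligation to meet footnote 4's abstinence standard. For women it also conflicts with criterion 6; for men it is the only definition.

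The effect is limited to the absence of a required commitment and reliability evaluation at entry. The documents do not give the number of patients concerned, so no rate or risk can be attached. No endpoint, power or analysis changes.

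The conclusion rests on reading criterion 6's two conditions as exhaustive (for the conflict in women) and on applying criterion 5's definition as stated (for both sexes). The consent pages are not available for review, so a contraception commitment there cannot be ruled out. It would lessen the consequence but would not repair the definition. The change is worth making because the present rule undercuts the protocol's own safeguard and costs very little to correct.

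**What to change.** - Delete the last four words of criterion 5's definition, the sexual-activity condition, for both sexes.
- For women, make criterion 6's definition the single one, stated as the only two routes out and keeping both its qualifiers (the stopping of exogenous treatments, and tubal ligation not counting). Refer to it in criteria 5 and 6, Table 2 footnote i, section 3.6.5.6 and every applicable-female line in 3.6.1.2, 3.6.1.3 and the End of Study visit.
- Treat sexual inactivity, in men and women, only as the abstinence method under footnote 4, with the reliability evaluation documented at entry.
- Optionally, reconfirm the contraceptive method of all patients of childbearing potential before the Week 24 infusion. This would improve the schedule generally and is not needed to cure the wording.

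The cost is a documented abstinence commitment for the affected patients and possibly a few urine tests at visits already scheduled. A woman infertile for some other reason would now fall under criterion 5 as well. On the natural reading of criterion 6 she is already in the class for testing.
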